### **Cover Sheet**

Choose ONE option from the following that is applicable to your study

If you are creating a new protocol, select "I am submitting a new protocol." As 5 Year Renewals are no longer required, this option remains for historical purposes.

I am proposing an amendment only to an existing protocol

### **Division & Personnel**

#### **Division**

What Area Group does the PI belong to?

What Division/Department does the PI belong to?

Anxiety Disorders Clinic

Within the division/department, what Center or group are you affiliated with, if any?

PTSD team

### **Unaffiliated Personnel**

List investigators, if any, who will be participating in this protocol but are not affiliated with New York State Psychiatric Institute or Columbia University. Provide: Full Name, Degrees and Affiliation. n/a

#### **Amendment**

Describe the change(s) being made

Currently, we assess participants at pre-intervention, post-intervention, 14-day follow-up and 30-day follow-up. For each step of the study the compensation fee is \$1.10.

We would like to add a 90-day follow-up, and conduct the same assessment as in 30-day follow-up and to add 1 item to inquire if the participant contacted mental health professionals.

In addition, the overall compensation for the study is now \$4.40.

Provide the rationale for the change(s)

We would like to understand longer-term effects of the intervention and if an observed change in help-seeking intentions is translate to change in help-seeking behavior.

Comment on the extent to which the proposed change(s) alter or affect risks/benefits to subjects We assess that there is no affect on risks/benefits to subject.

Comment on if the proposed change(s) require a modification to the Consent Form (CF)

We don't think a change in CF is needed.

#### **Procedures**

To create the protocol summary form, first indicate if this research will include any of the following procedures

✓ Internet-based Data Collection or Transmission

### **Population**

Indicate which of the following populations will be included in this research

✓ Adults

Adults over 50

# **Research Support/Funding**

Will an existing internal account be used to support the project?

Yes

Describe internal account

Account RFMH: 2801D

Is the project externally funded or is external funding planned?

### **Study Location**

Indicate if the research is/will be conducted at any of the following 
✓ NYSPI

This protocol describes research conducted by the PI at other facilities/locations No

# Lay Summary of Proposed Research

Lay Summary of Proposed Research

The COVID-19 outbreak exceeds scope and magnitude of most previous disasters over the last 100 years, and has a significant impact upon mental health. It entails a blend of risk factors for both acute and long-term mental health problems. Data that is started to emerge from the COVID-19 outbreak, suggest that front lines health workers (doctors; nurses) are particularly at risk for depression, anxiety and PTSD. Others may develop moral injury, a profound psychological distress which results in actions, or the lack of them, which violet one's moral or ethical code. Given the magnitude of the COVID-19 outbreak, its risk to physical and mental health, an effective and timely response is essential to address the psychosocial needs associated with the ongoing exposure to disease, death, and distress among health care providers, across low and high risks areas.

Many health care providers reluctant to seek support from friends and family, as well as mental health care due to stigma and fear. Despite enduring symptoms, they may wait months to years before they seek help. Applying strategies to reduce stigma and fear towards mental health care and improve help seeking behavior may ameliorate impaired functioning and reduce risks for long-term psychiatric illness. Studies have shown that social contact is the most effective type of intervention to reduce stigma-related attitudes and to improve help-seeking behavior. The overarching goal of this study is to examine the efficacy of video intervention in reducing stigma and fear, and improving help seeking behavior among health care providers (N=1,200), with pre-, post- and follow up assessments (day 14, day 30 and day 90). Participants will be randomly assigned to either a) a video-based intervention (day 1 and a "booster intervention" of the same content on day 14 of the study) featuring the personal story of a health care provider with COVID-19, his struggles and barriers to care, (b) video-based intervention (day 1 only), and a written description of the same story on day 14 (c) no-intervention control arm (questionnaires only). We aim to (1) determine whether video-based intervention reduce stigma and fear, and increase helpseeking behavior in relation to COVID-19 among health care providers, and (2) compare high risk areas (e.g., NY) to low risk areas (e.g., Montana) on intervention outcomes, and (3) test whether symptoms of depression, anxiety, PTSD and Moral Injury, that will be measured by Patient Health Questionnaire (PHQ-9), Generalized Anxiety Disorder (GAD-7), the Primary Care PTSD Screen for DSM-5 (PC-PTSD-5), and the Moral Injury Events Scale (MIES) would change overtime.

# **Background, Significance and Rationale**

Background, Significance and Rationale

Coronavirus disease 2019 (COVID-19) has widely and rapidly spread around the world. To effectively respond to the COVID-19 outbreak, various governments have implemented rapid and comprehensive public health emergency interventions that include social restrictions and quarantines, which is the separation and restriction of movement of people who might have been exposed to the virus. While the physical risk (e.g. pneumonia, respiratory breakdown) is getting the most scientific and clinical attention, this outbreak also has significant mental health risks and extreme psychological fear-related responses. Psychological responses to previous large-scale outbreaks, particularly to the Ebola Virus Disease (EVD) epidemic during 2014-2016, provide insight into the potential impact of rapidly spreading diseases on mental health problems (1). During the Ebola outbreak, fear-related behaviors such as stigmatizing infected survivors and ignoring medical procedures impeded public health efforts and negatively affected recovery of survivors (2). Anxiety, posttraumatic stress disorder (PTSD), and depression were found in nearly half of the EVD survivors and their contacts (2).

The COVID-19 outbreak exceeds scope and magnitude of most previous disasters over the last 100 years. It entails a blend of risk factors for both acute and long-term mental health problems. Data that is started to emerge from the COVID-19 outbreak, suggest that front lines health workers (doctors; nurses) are particularly at risk. A recent study (3) in 1257 health care workers from 34 hospitals, conducted between January 29 to February 3, 2020, revealed that more than half (50.4%) of the health workers were screened positive for depression, 44.6% for anxiety, and 34.0% for insomnia. Consistent with previous disaster studies (4) a dose response relationship was found between level of exposure and outcomes. Others may develop moral injury, a profound psychological distress which results in actions, or the lack of them, which violet one's moral or ethical code (5,6). Given the magnitude of the COVID-19 outbreak, its risk to physical and mental health, an effective and timely response is essential to address the psychosocial needs associated with the ongoing exposure to disease, death, and distress among health care providers, across low and high risks areas.

Many health care providers reluctant to seek support from friends and family, as well as mental health care due to stigma and fear (e.g., "it would be too embarrassing", "I would be seen as week")(4). Despite enduring symptoms, they may wait months to years before they seek help (7). Among reasons to avoid seeking mental health care, individuals report mistrust in mental health providers, being seen as weak or stereotyped as "crazy", and a belief that they may be responsible for having mental health problems (8.9). Applying strategies to reduce stigma and fear towards mental health care and improve help seeking behavior may ameliorate impaired functioning and reduce risks for long-term psychiatric illness. Studies (10) have shown that social contact is the most effective type of intervention to reduce stigmarelated attitudes and to improve help-seeking behavior. Social contact involves interpersonal contact with members of the stigmatized group: members of the general public who meet and interact with individuals who suffer from stress, fear, depression or anxiety and seek mental health care, are likely to lessen their stigma. Corrigan (11) identified the most important ingredients of contact-based programs: an empowered presenter with lived experience who attains his/her goals (e.g., "I was able to fight the depression/distress that I had following the COVID-19"). While both direct, in-person social contact and indirect, video-based social contact have effectively improved attitudes toward mental issues and care, the latter can be implemented on a larger scale, use a minimal resource and easily disseminated (12-14).

## **Specific Aims and Hypotheses**

Specific Aims and Hypotheses

The overarching goal of this study is to examine the effect of video intervention in reducing stigma and fear, and improving help seeking behavior among health care providers across the US.

In a sizable randomized controlled trial (N=1,200, general population), with pre-, post- and follow-up assessments (day 14, day 30 **and 90 day**), we aim to (1) determine whether video-based intervention reduce stigma and fear, and increase help-seeking behavior in relation to COVID-19 among health care providers, and (2) compare high risk areas (e.g., NY) to low risk areas (e.g., Montana) on intervention outcomes, and (3) test whether symptoms of depression, anxiety, PTSD and Moral Injury, that will be measured by Patient Health Questionnaire (PHQ-9), Generalized Anxiety Disorder (GAD-7), the Primary Care PTSD Screen for DSM-5 (PC-PTSD-5), and the Moral Injury Events Scale (MIES) would change overtime.

Hypotheses: We hypothesize that (1) the brief video intervention will have greater impact in reducing stigma and fear, and in increasing help-seeking behavior in relate to COVID-19 than the control groups in comparison to pre-intervention and to non-video conditions, (2) High risk areas will have increased baseline rates of anxiety, depression and PTSD, and (3) the brief video is expected to have greater impact in reducing symptoms of depression, GAD and PTSD.

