#### Statistical Analysis Plan

Data will be analyzed using SPSS Statistics 26.0 for Mac. We will use Pearson's chi-squared ( $\chi 2$ ) and one-way analysis of variance (ANOVA) to compare demographic variables and baseline psychopathological characteristics of the three groups. To represent within-participant dependencies in the models, we will specify an unstructured correlation matrix. We will first apply a full factorial model across the four time points (baseline, post-intervention, 14- and 30-day follow-ups) for treatment-seeking intentions and three time points (baseline, 14- and 30-day follow-ups) for clinical symptoms. Group × time interaction terms will test the intervention effect hypothesis of greater treatment-seeking in the two video groups. If between-group differences are found, post hoc tests will be used to compare each group pair, including the overall changes from baseline assessment to 30-day follow-up. Effect sizes will be reported using Cohen's d when appropriate. All statistical tests will be two-sided, using  $\alpha < 0.05$ .

Protocol Title: Version Date: The COVID-19 and healthcare workers: an 10/20/2020

active intervention

Protocol Number:

8032

Clinic: First Approval:

07/13/2020 **Anxiety Disorders Clinic** 

**Expiration Date:** No Expiration

Contact Principal Investigator: Principal Investigator: [name], PHD

**[name]** Email:

[contact]

Co-Investigator(s): [contact] [name], MPH

> Research Chief: [name]

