#### Inclusion/Exclusion Criteria

Name the subject group/sub sample

AMT participants

Create or insert table to describe the inclusion criteria and methods to ascertain them

Study Criteria Methods of Ascertainment

Healthcare AMT setting will be used to limit responders to of

workers healthcare workers only

80>Age>18 AMT requires responders to be at least 18 years old and

lower than 80

[name]

English AMT settings will be used to limit responders to English

speakers speakers only

US residents AMT settings will be used to limit responses to users in

US only

Create or insert table to describe the exclusion criteria and methods to ascertain them

Study Criteria Methods of Ascertainment

Age<18 AMT requires responders to be at least 18 years old

Age>80 AMT settings will be used to limit the age to 80 years old Non healthcare AMT settings will be used to ensure that only healthcare

workers will participate

Non English AMT settings will used to ensure that only English

speakers speakers will participate.

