#### **Assessment Instruments**

Create a table or give a brief description of the instruments that will be used for assessment Questions for the pre- and post-intervention (day 1) and follow-ups (day 14, day 30 and **day 90**). Baseline Questionnaire (will be conducted pre intervention only) will include four questions regarding demographics (age, sex, ethnicity and race). Based on previous studies it is estimated the response time will be around 30 seconds.

Three questionnaires will be conducted at pre- and post-intervention (day 1) and follow-up (day 14, day 30 and day 90):

- 1. Attitude towards COVID-19 attitude towards COVID-19 questions were adapted from a measure created by Berger et al. about stigma and fear towards people with HIV. The questionnaire will include six questions and based on previous studies it is estimated the response time for 50 seconds.
- 2. Attitude towards seeking help Attitude towards help seeking will be based on the ATSPPH-SF (Attitudes Towards Seeking Professional Psychological Help Scale), and will include 5 questions (0-disagree, 3-agree). One table will be created to include all 5 questions in one screen. Based on previous studies it is estimated the response time will be around 40 seconds.
- 3. COVID-19 related behaviors and experiences was developed by the researchers and will include six questions regarding social media use, news consumption, social contact, previous contact with a known COVID-19 patient and if the participant has been tested for COVID-19. It is estimated the response time will be around 50 seconds.

Three questionnaires will assess clinical symptoms and will be conducted at pre-intervention (day 1) and follow-up (day 14, day 30, and **day 90**):

- 1. GAD-7 questionnaire will include 7 questions that assess anxiety
- 2. PHQ-9 questionnaire will include 9 questions to assess depression
- 3. Primary Care PTSD screen for DSM-5 will include 5 yes/no questions to assess PTSD. Three tables will be created, one for each questionnaire. Based on previous studies it is estimated the response time will be 150 seconds.

One questionnaire will assess Moral Injury (MIES), and includes 9 items (50 seconds).

In sum, the estimate time for day 1 (pre and post intervention) is 7-9 minutes for intervention groups and 5-7 minutes for control. The estimate time for each follow up is 4-7 minutes (days 14, 30 and 90).

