#### Risks/Discomforts/Inconveniences

Risks that could be encountered during the study period

Breach of confidentiality is the main risk of the study. Another potential risk is that participants may experience mild psychological distress when answering questions about COVID-19, due to its sensitive nature.

Describe procedures for minimizing risks

For both of these risks, participants will be reminded that their responses are completely anonymous and that they are free to select "prefer not to answer" if they do not wish to answer a question or end their study participation at any time. Further ways to address the risk of breach of confidentiality are discussed in the Methods to Protect Confidentiality section.

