## **Methods to Protect Confidentiality**

Describe methods to protect confidentiality

AMT protects confidentiality in keeping with the Amazon.com privacy policies. No identifiable information concerning participants' responses is shared with anyone outside the research team. The investigators of this research will only have access to the de-identified responses and associated demographic data of the respondents. We will not use any identifying information as IP addresses, and therefore will be unable to identify any individual respondent. Hence, we are requesting a waiver of the documentation of consent.

Will the study be conducted under a certificate of confidentiality?

No

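### Aim 2 and Hypothesis 2 (high- versus low-risk areas) cannot be answered as the plan is described: no described item records location, and the SAP has no area term

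*Combined protocol and SAP*

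**What the plan says.** The Specific Aims and Hypotheses section, and the Lay Summary in the same terms, set as Aim 2 to "compare high risk areas (e.g., NY) to low risk areas (e.g., Montana) on intervention outcomes". Hypothesis 2 states that "High risk areas will have increased baseline rates of anxiety, depression and PTSD".

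The data to be collected are described under Assessment Instruments. The baseline form "will include four questions regarding demographics (age, sex, ethnicity and race"). The COVID-19 behaviours form has "six questions regarding social media use, news consumption, social contact, previous contact with a known COVID-19 patient", and COVID-19 testing. The remaining instruments are the attitude and help-seeking scales, GAD-7, PHQ-9, PC-PTSD-5 and MIES. The question added at day 90 concerns medication, psychological treatment and contact with professionals.

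On location, the Inclusion/Exclusion Criteria say that "AMT settings will be used to limit responses to users in" the US. Methods to Protect Confidentiality says "We will not use any identifying information as IP addresses".

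The SAP will "compare demographic variables and baseline psychopathological characteristics of the three groups" and then test group × time interactions. It does not mention area, region or risk level.

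**The concern.** An aim needs three things: a variable that measures it, a rule that defines it and an analysis that tests it. The area comparison appears to have none of them.

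The two statements also ask different questions. Hypothesis 2 is a cross-sectional comparison of baseline symptom rates between areas. Aim 2 asks whether outcomes of the intervention differ by area, which is an interaction of area with randomised group over time. A baseline table by randomised arm and a group × time test answer neither.

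Location cannot be reconstructed at analysis once the survey waves are finished. If the classification is left open until data are in hand, the cut between high and low risk could be chosen after seeing which cut gives a difference.

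**Working it through.** **Step 1. Does any described source give location?**

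| Source (section) | Content described | Location? |
|---|---|---|
| Baseline form (Assessment Instruments) | Four questions, all four named | No |
| COVID-19 behaviours form (same) | Six questions, five topics named | None named; one question unaccounted for |
| Attitude, help-seeking, symptom and moral-injury scales (same) | Attitudes, symptoms, moral injury | No |
| Added day-90 question | Treatment and contact with professionals | No |
| Platform settings (Inclusion/Exclusion Criteria) | Restriction to US users | Country only |
| IP address (Methods to Protect Confidentiality) | Not used | No |

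No described item records state or area, so 0 of 1,200 participants can be classified on the plan as written.

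**Step 2. Is high or low risk defined?** New York and Montana are given as examples. There is no threshold, date window or data source, and nothing assigns the other states.

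**Step 3. Does the SAP contain the analysis?** It has a baseline comparison by randomised arm and a group × time interaction. It has neither a baseline comparison by area (Hypothesis 2) nor an area × group × time term (Aim 2).

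**Step 4. What could be detected if location were added?** The plan gives no power figure to reproduce, so this is an illustration.

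- From the documents: N = 1,200, three arms, two-sided 0.05, and 50.4% screening positive for depression in a study cited in the Background.
- Assumed: equal arms, 80% power, no dropout, and a low-risk share *s* of 50%, 25%, 10% or 5%.

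The multiplier is 1.960 + 0.842 = 2.802.

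*Baseline rate difference:* 2.802 × √[0.504 × 0.496 × (1/(N·s) + 1/(N·(1−s)))]. At N = 1,200 and s = 0.50 this is 2.802 × √[0.250 × (1/600 + 1/600)] = 0.081.

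*Area × pooled-video interaction at one time point, in SD:* 2.802 × √[1/(2N/3) + 1/(N/3)] × √[1/s + 1/(1−s)]. At N = 1,200 the first two factors give 2.802 × √(1/800 + 1/400) = 0.172, which is the overall pooled contrast. The last factor is 2.00, 2.31, 3.33 or 4.59 for the four shares.

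*Area × one video arm versus control:* replace the arm factor by √(2/400), giving 0.198 for the plain contrast, then apply the same last factor.

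| Low-risk share | Baseline difference, N = 1,200 | Pooled interaction, N = 1,200 | Single-arm interaction, N = 1,200 | Baseline difference, 600 classified | Pooled interaction, 600 classified |
|---|---|---|---|---|---|
| 50% | 8.1 points | 0.34 SD | 0.40 SD | 11.4 points | 0.49 SD |
| 25% | 9.3 points | 0.40 SD | 0.46 SD | 13.2 points | 0.56 SD |
| 10% | 13.5 points | 0.57 SD | 0.66 SD | 19.1 points | 0.81 SD |
| 5% | 18.6 points | 0.79 SD | 0.91 SD | 26.2 points | 1.11 SD |

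The 600 columns assume that only half the sample can be classified. Letting the variance follow each area's own rate lowers 18.6 to between 17.7 and 18.2 points.

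For change from baseline, the pooled interaction is multiplied by √[2(1−ρ)]. At N = 1,200 and a 50% share it is 0.41, 0.34 or 0.27 SD for assumed correlations ρ of 0.3, 0.5 or 0.7.

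**The case against.** The strongest reply is that location may be collected without being described. The behaviours form has one question with no named topic, and the form is not reproduced. The platform already screens on several characteristics and the investigators receive associated demographic data, so state might arrive by that route. The sentence on IP addresses is about not identifying individuals, not about coarse location. This stands as a limit: an undescribed item cannot be excluded, and the finding speaks only to the plan as described. If such an item exists, describing it closes the data gap, but the missing definition and the missing analysis remain.

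The SAP also calls its model full factorial without listing the factors. Since area is named nowhere in the SAP, that phrase cannot be read as including it.

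The power figures are open to criticism. They rest on assumed shares and allocation, and they use one-degree-of-freedom contrasts rather than the full three-way term. Pooling the video arms is also kinder than the pairwise post hoc comparisons that the SAP specifies, which is why the single-arm column is shown. It is fair too that low power describes the interaction better than the baseline comparison: with an even split and everyone classified, 8.1 points is a reasonable detectable difference. None of this affects the defect, which does not depend on these figures.

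**Conclusion.** The concern holds. As described, the plan has no variable, no definition and no analysis for the area comparison, so one of three aims and one of three hypotheses would get no answer. The randomised comparison and its group × time test are untouched, so this should be fixed but does not threaten the main result.

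Adding location would make the baseline comparison workable if low-risk areas are well represented. The interaction would remain weak: its detectable size is at least twice that of the corresponding overall contrast, and more than four times at a 5% low-risk share. Aim 2 should therefore be secondary even after repair. The conclusion assumes that the described instruments are complete; the detectable differences also rest on the assumptions listed in the working.

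**What to change.** Choose one of two routes.

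**(a) Support the aim.**

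- Add one state-of-residence question at baseline. State is the level of the protocol's own examples and carries less re-identification risk than county, though it hides variation within a state.
- In the remaining follow-up surveys, ask people already enrolled for their state at enrolment.
- Classify every state by a COVID-19 incidence threshold over a stated date window from a named source, fixed before outcome data are examined. The Amendment section indicates that assessments are under way, so state whether any outcome data have already been seen.
- In the SAP, compare baseline GAD-7, PHQ-9 and PC-PTSD-5 by area, giving the cut-off for each scale, because Hypothesis 2 concerns rates. Add an area × group × time term to the outcome model for Aim 2, labelled secondary with limited power.

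The cost is one multiple-choice item, a paragraph in the SAP and an amendment of the kind already submitted for the day-90 survey. The extra field must be covered in the confidentiality section, since the protocol says "Breach of confidentiality is the main risk of the study". Participants who have finished all waves, or who do not answer a later one, stay unclassified. The area analysis would then rest on later responders among those already enrolled, and this should be reported.

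**(b) Withdraw it.** Remove Aim 2 and Hypothesis 2 by amendment and state that location was not collected. This is a text change only, but it gives up one aim and one hypothesis.

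If a location item already exists, describe it; the classification rule and the two analyses are still needed.
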